It should be noted that these outcomes are comparable to those reported in the literature for percutaneous SFA interventions.

Table 8: STP 115 Safety Outcomes

Safety Outcomes	30-Day Treated Subjects N = 59 ¹	6-Month Treated Subjects N = 59 ¹	12-Month Treated Subjects N = 35
Major Adverse Events (MAE)², (% n/N)	3.4% (2/59)	10.2% (6/59) ⁶	14.3% (5/35)
Major Adverse Clinical Events (MACE)³, (% n/N)	3.4% (2/59)	10.2% (6/59) ^{6,7}	14.3% (5/35)
Deep Vein Thrombosis (DVT)⁴, (% n/N)	0% (0/59)	0% (0/59)	0% (0/35)
Major Bleeding⁵, (% n/N)	0% (0/59)	0% (0/59)	0% (0/35)

¹ Excludes 1 subject who did not receive an implant and withdrew from the study post-discharge.

² Composite endpoint defined as death, target limb amputation and target vessel revascularization as adjudicated by Independent Medical Review.

³ Composite endpoint defined as death, target limb amputation, TVR, DVT of ipsilateral limb or bleeding event requiring transfusion > 2 units of packed red blood cells as adjudicated by Independent Medical Review.

⁴ Defined as a symptomatic blood clot (thrombus) in the ipsilateral limb as adjudicated by Independent Medical Review.

⁵ Defined as transfusion of >2 units packed red blood cells (PRBC) through discharge as adjudicated by Independent Medical Review.

⁶ All subjects experienced target vessel revascularizations (TVR).

⁷ One subject experienced 2 events (TVR and acute limb ischemia).

Comparison of MAE Rates at 30 days and 12 Months to the Viabahn Stent Graft

MAE, defined similarly to the PQ Bypass study (all cause death, TVR and amputation of index limb) through 30 days and 12 months for the Viabahn Endoprosthesis, as reported in the literature, are presented below in **Table 9** and **Table 10**. Only studies which reported all individual events included in the MAE composite were included, so a sum total MAE rate could be calculated.

MAE rates in studies which reported on the Viabahn stent graft ranged from 0.0% to 11.1% at 30 days and from 32.5% to 50.0% at 12 months.

Table 9: Comparison of PQ Bypass 30 Day MAE Rates to Viabahn 30 Day MAE Rates as Reported in the Literature

Lead Author - Year	30 Day Death (%)	30 Day TLR/TVR (%)	30 Day Amputation (%)	Total 30 Day MAE ¹ (%)
Schneider_2011 ¹	0.0%	7.4%	3.7%	11.1%
Saxon_2013 ²	0.0%	0.8%	0.0%	0.8%
Lammer_2013 ³	0.0%	1.3%	0.0%	1.3%
Zeller_2014 ⁴	0.0%	0.0%	0.0%	0.0%
PQ Bypass Study	0.0% (0/59)	3.4% (2/59)	0.0% (0/59)	3.4% (2/35)

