5.2 Study Endpoints

Primary Safety Endpoint:

The primary safety endpoint for this study is freedom from a major adverse event (MAE) at 30 days post procedure. An MAE is defined as TLR, amputation of the treated limb, or death.

Primary Effectiveness Endpoint:

The primary effectiveness endpoint is defined as stent patency as evidenced by a peak systolic velocity ratio (PSVR) < 2.5 from DUS obtained within the 12 month visit window with no clinically driven re intervention within the stented segment.

Secondary Safety Endpoints:

Secondary safety endpoints will be evaluated and include:

1. The combined rate of death at 30 (± 7) days, target lesion revascularization (TLR), index limb amputation, and an increase in Rutherford Becker Classification by 2 classes (comparing pre to post procedural assessments) at 12 months.
2. Major adverse vascular event (MAVE) at 30 days, 6 months (180 ± 14 days) and 12 months (360 ± 30 days) defined as stent thrombosis, target limb amputation, clinically apparent distal embolization, defined as causing end organ damage (e.g. lower extremity ulceration, tissue necrosis, or gangrene), procedure related arterial rupture, acute limb ischemia, or bleeding event requiring transfusion.
3. The combined rate of serious procedural adverse events, including death, myocardial infarction, index limb amputation, and access site and treatment site complications requiring surgery, blood transfusion (>2 units of PRBC), or prolonged hospital stay within 30 days of the index procedure.

Secondary Effectiveness Endpoints:

1. Acute technical (lesion) success, procedural success and device success.
2. Ankle Brachial Index (ABI) and Toe Brachial Index (TBI) at 1, 6 and 12 months.
3. Target vessel revascularization (TVR) at 6 and 12 months.
4. Limb ischemia by Rutherford Becker Classification at Baseline, 1, 6, and 12 months.
5. Number of any type of index limb amputations at 6 and 12 months.
6. Absolute Claudication Distance as measured by the Exercise Tolerance Test (TASCI) assessed in 100 subjects at baseline, 1, 6, and 12 months.
7. Target lesion revascularization (TLR) at 1, 6 and 12 months.

8. The rate of primary assisted patency through follow up defined as: revascularization of non occlusive (<99%) stenosis within the stent graft or immediately above or below the treated arterial segment with less than 50% residual stenosis.

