11.0 ENDPOINTS AND STATISTICAL ANALYSIS PLAN**11.1 Endpoints Analyses and Reporting of Results**

The study objective is to assess the safety and performance of the PQ Bypass Stent Graft System to access, deliver guidewires and implant stent grafts. The statistical methods for the primary endpoints are pre specified in this analysis plan and cannot be changed at the time of analysis.

All subjects will be followed on an intent to treat basis. The device performance will be assessed based on a per protocol analysis of the primary safety and effectiveness endpoints. An Intent to treat analysis, along with other secondary analyses, will also be completed and reported. Demographic, baseline clinical and disease characteristics, procedural results and primary, secondary and all additional endpoints will be summarized using descriptive statistics. All statistical analyses will be performed using SAS for Windows version 9.1 or higher.

As noted above, up to 65 subjects with a documented untreated, atherosclerotic lesions of the native superficial femoral artery (SFA) or the superficial femoral and proximal popliteal arteries, suitable for treatment with PQ Bypass Stent Graft may be enrolled in the study to ensure an appropriate sample size of 60 evaluable subjects post treatment.

- Safety assessment will be achieved by recording and measuring Major Complication rates/Serious Adverse Event rates associated with the PQ Bypass stent grafts. The primary safety endpoint (MAE) and MAVE will be presented using descriptive statistics at various time intervals. Using the Wilson Method, the one sided upper 95% confidence bound will be calculated and presented.
- The primary performance hypothesis will be tested by calculating the one sided 95% lower confidence limit for the rate of successful performance using the Wilson Method. If the lower limit exceeds the performance goal rate of 70% the null hypothesis will be rejected and the endpoint will be met. In addition to hypothesis testing, descriptive statistics of the primary performance endpoint will include the total number and percentage of patent PQB grafts.
- Descriptive statistics of the primary performance endpoint which includes total number of patent PQ Bypass grafts, percentage of patent PQ Bypass grafts, and the one sided 95% CI of the percentage using the Score approximation will be presented. The lower bound of the one sided 95% CI will be will be calculated and presented.

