11.2 Primary Safety Endpoint Reporting

The primary safety endpoint is the rate of Major Adverse Events (MAEs) at 30 days. The number and percent of subjects that experience at least one MAE through 30 days post procedure will be reported along with the upper one sided 95% confidence limit. In addition the number and percentage of subjects reporting MAEs and MAVEs will be presented using descriptive statistics at various time intervals, combined and by type of event. The confidence intervals will be calculated using the Wilson method.

11.3 Primary Performance Endpoint Reporting:

The primary performance hypothesis will be tested by calculating the one sided 95% lower confidence limit for the rate of successful performance using the Wilson Method. If the lower limit exceeds the performance goal rate of 70% the null hypothesis will be rejected and the endpoint will be met. In addition to hypothesis testing, descriptive statistics of the primary performance endpoint will include the total number and percentage of patent PQB grafts.

11.4 Secondary Endpoint Analysis:

The secondary endpoint of primary assisted and secondary patency will be summarized using Kaplan Meier survival analysis. Life tables will be created and a Kaplan Meier survival curve will be presented.

The secondary endpoints inclusive of Procedural Success, Clinical Success and Technical Success will be summarized by providing point estimates, number of subjects, and 95% confidence bounds calculated using the Score approximation.

11.5 Demographic, procedural and safety data:

Demographic and baseline clinical and disease characteristics will be summarized in tables. For continuous variables the summary will include number, mean, and standard deviation and 95% confidence intervals. Summaries for categorical variables will include the number and percent of subjects in each category.

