11.6 Imputation for Missing Data

Imputations for missing data in (e.g. withdrawn subjects, loss to follow up, missing data) will not be performed. Analyses will be performed with all available data only.

12.0**ADVERSE EVENTS**

The occurrence of Adverse Events will be monitored during this study. All Adverse Events will be recorded on the Adverse Event Form at onset and at each follow up visit until resolved. To meet the objectives of this study, the following definitions will apply. (Definitions reference ISO 14155:2011 01). Potential adverse events associated with use of the SGS include, but are not limited to the following:

 • Access site hemorrhage or hematoma • Access site pain/infection • Acute vessel closure • Aneurysm or pseudoaneurysm formation • Arteriovenous (AV) fistula • Death • Device failure • Embolism • Fever/pain in absence of infection • Infection 	
 • Inflammation • Malposition • Myocardial infarction • Radiation injury • Renal insufficiency/failure due to excessive contrast load • Sepsis • Shock • Side branch occlusion • Stenosis or Occlusion • Thrombosis • Vessel dissection, perforation or wall trauma
--	--

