14.2 Clinical Data Management

Software

This study will utilize electronic data capture (EDC), allowing the data to be entered directly into the computerized system by the clinical site personnel. The Medrio electronic data capture software will be used. This software was developed and validated by Medrio Incorporated. The specific study set up within the software will be the subject of user acceptance testing and is not released for use in the study until it has successfully passed this testing.

Security

Hosting is provided by Medrio Inc. and the data entered on the electronic case report forms (eCRFs) along with applicable metadata is transmitted using 128 bit SSL and 1024 bit RSA public keys. The server on which the data will be stored resides within a secure data center with security guards, electronic access controls and digital video monitoring as well as Cisco firewalls and advanced intrusion detection/prevention systems. Access to the study EDC system will be limited to authorized users with permission levels granted based on the user's role in the study. Each user is given a unique user ID and generate their own private

Query Management

Queries are generated and managed within the EDC system. Data checks, including those that detect missing or inconsistency entries, will be programmed into the system and will automatically be generated upon data entry. Manual queries may also be generated by the monitors, CRAs or data management personnel as necessary. Sites can respond to an automatic system generated query by making an update to the data and/or providing a textual response to the query. Query responses are reviewed and closed out by the monitor, CRA or data management personnel.

Database Closure and Export for Analysis

The primary clinical study report will be generated once all necessary patients have reached the primary efficacy follow up of 12 months. A database snapshot will be taken at this time for analysis. Data will be reviewed per the data snapshot checklist that will list the data cleaning activities required. All data is exported into SAS format for analysis by the study statistician and to be archived. Once all follow up has been completed and the database closure checklist completed, the EDC system study data and metadata will be exported and archived. All CRF data will be exported into SAS format for analysis and archive.

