15.0 PROTOCOL DEVIATIONS

A protocol deviation is defined as an event where the Investigator or site personnel did not conduct the study according to the protocol.

Investigators shall be required to obtain prior approval from PQ Bypass Clinical Director before knowingly deviating from the protocol, except where necessary to protect the life or physical well being of a subject in an emergency. Such approval shall be documented in writing and maintained in clinical study management and Investigator files. Prior approval is generally not expected in situations where unforeseen circumstances are beyond the Investigator's control, (e.g., subject was not available for scheduled follow up office visit, blood sample lost by laboratory, etc.); however, the event is still considered a deviation and will be reported via the appropriate CRF.

Deviations must be reported to PQ Bypass regardless of whether medically justifiable, pre approved by PQ Bypass or taken to protect the subject in an emergency. Subject specific deviations will be reported on the Protocol Deviation case report form. Non subject specific deviations, (e.g., unauthorized use of an investigational device outside the study, unauthorized use of an investigational device by a physician who has not signed an Investigator agreement or not been trained in the use of the device, etc.), will be reported to PQ Bypass. Investigators will also adhere to procedures for reporting study deviations to their EC and CA, where required, in accordance with their specific reporting policies and procedures.

Regulations require that Investigators maintain accurate, complete and current records, including documents showing the dates of and reasons for each deviation from the protocol.

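### Both primary endpoints, including the only hypothesis test, rest on a per-protocol set that the plan neither defines nor requires to be fixed before the 12-month data are seen

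*Combined protocol and SAP*

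**What the plan says.** Section 11.1 puts both primary endpoints on a per-protocol footing: "The device performance will be assessed based on a per protocol analysis of the primary safety and effectiveness endpoints". It continues: "An Intent to treat analysis, along with other secondary analyses, will also be completed and reported". The decision rule, given in sections 11.1 and 11.3, uses a one-sided 95% Wilson lower limit: "If the lower limit exceeds the performance goal rate of 70% the null hypothesis will be rejected and the endpoint will be met". Sections 11.2 and 11.3 name no analysis population.

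The per-protocol set has no membership rule in section 11, section 15 or the definitions in section 19. Section 15 comes closest: "A protocol deviation is defined as an event where the Investigator or site personnel did not conduct the study according to the protocol". It does not grade deviations or say which of them remove a subject from analysis. Section 11.1 also speaks of 60 evaluable subjects, and its sample-size paragraph of 50, without defining evaluable.

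On missing data, section 11.6 says: "Analyses will be performed with all available data only". The patency endpoint in section 5.2 requires a PSVR below 2.5 "from DUS obtained within the 12 month visit window with no clinically driven re intervention within the stented segment". On timing, section 14.2 says: "The primary clinical study report will be generated once all necessary patients have reached the primary efficacy follow up of 12 months". A database snapshot is taken then, but no step before it fixes who is in the primary set.

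**The concern.** A confidence limit with an open denominator is not a fully specified test. Section 11.1 says the statistical methods for the primary endpoints cannot be changed at analysis, but that sentence does not reach the choice of subjects. With one arm and no comparator, whoever settles the per-protocol list at the snapshot may already know which grafts failed. Because any departure from the protocol is a deviation, a reason to exclude could be found for many subjects.

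There is a smaller, second gap. A subject with an early clinically driven re-intervention and no duplex scan in the 12-month window is a failure on the best reading of section 5.2. Read together with the available-data rule in section 11.6, the text does not rule out treating that subject as missing.

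At stake is the study's only confirmatory claim. For safety, the estimate and its bound are at stake, since the MAE rate is descriptive.

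**Working it through.** **Inputs.** From section 11.1: performance goal 70%, assumed true patency 85%, one-sided alpha 0.05, power 80%, stated requirement 50, target of 60 evaluable, up to 65 enrolled. The number of failures excluded is not in the documents; it is assumed here to be 0 to 3.

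**The plan's own figure.** n = [1.645·√(0.70·0.30) + 0.842·√(0.85·0.15)]² / 0.15² = 49.4, rounded up to 50. The stated 50 reproduces under this normal approximation, so the sample-size arithmetic is not the problem. (An exact binomial search gives 49.)

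**Decision rule.** The Wilson lower limit for x patent of n, with p = x/n and z = 1.645, is

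L = [p + z²/2n − z·√(p(1−p)/n + z²/4n²)] / (1 + z²/n).

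- 47/60: p = 0.7833; L = (0.7833 + 0.0225 − 0.0903)/1.0451 = 0.685. Misses.
- 47/58 (the same 47 patent grafts, two failures excluded): p = 0.8103; L = (0.8103 + 0.0233 − 0.0878)/1.0466 = 0.713. Passes.
- 46/60: L = 0.667, misses. 46/57: L = 0.708, passes.
- 51/65: L = 0.690, misses. 51/64: L = 0.703, passes.

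The smallest passing counts are 48 at n = 60, 48 at 59, 47 at 58 and 46 at 57; and 52 at n = 65, 51 at 64, 51 at 63 and 50 at 62.

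**Chance of passing when true patency is exactly 70%.** Let X ~ Bin(N, 0.70). If k failures are excluded, the test passes when X reaches the smallest passing count for N − k.

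| Failures excluded | N = 60 | N = 65 |
|---|---|---|
| 0 | 5.7% | 4.8% |
| 1 | 5.7% | 8.5% |
| 2 | 10.0% | 8.5% |
| 3 | 16.2% | 13.9% |

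The steps are uneven because the passing count moves in whole subjects. At N = 60, one exclusion changes nothing, since 48 are still needed at 59. The 5.7% with no exclusions is a property of the Wilson rule at that size, not of the analysis set.

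**Exclusion unrelated to outcome.** The test is then simply run at the smaller n: 4.1% at n = 58 and 4.9% at n = 57. There is no inflation and the estimate is unbiased.

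**Safety, same kind of illustration.** 4/60 with an MAE is 6.7%, Wilson upper limit 14.0%. With two event subjects excluded, 2/58 is 3.4%, upper limit 9.9%. No decision hangs on either.

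**Power of the Wilson rule at 85% by number analysed.** For 57 to 65 subjects it runs from 83.4% (n = 59, 48 needed) to 91.0% (n = 64, 51 needed). At n = 50 (41 needed) it is 79.1%, and at n = 51 (42 needed) 77.3%.

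**The case against.** The promised intent-to-treat report would expose a per-protocol result that differs from it. Eligibility is confirmed before device insertion (section 6.2), enrolled subjects are to complete follow-up for safety (section 6.4), and the protocol summary provides an independent core laboratory and event adjudication. All of this stands as mitigation. None of it settles who is in the primary set: intent to treat is itself undefined and carries no success rule, and independent reading protects the outcome, not the denominator.

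A reader might infer that the plan lets re-intervened subjects drop out. That goes too far. The endpoint has two conditions, and a re-intervened subject cannot meet the second whatever the scan shows. The text is open to the other reading but does not direct it.

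A reader might also infer that the sponsor intends to remove failures. The documents do not say so, and the reference in section 14.2 to necessary patients is a trigger for the report, not an analysis set. Nor is a higher chance of passing at a true patency of 80% evidence of harm: the null is false there and passing is correct. Only the 70% row measures false success.

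Finally, the proposed set still omits non-implanted subjects and those with no scan and no earlier failure. That is so. The reason for the first is that the endpoint concerns a stented segment, which non-implanted subjects do not have. Both omissions are written in advance, need no judgement about deviations, and are covered by a sensitivity analysis.

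**Conclusion.** The concern holds as an omission with consequences. The primary analysis set for both endpoints is undefined, is not required to be fixed before the snapshot, and governs the only hypothesis test. That the definition is absent is clear from the text. The size is illustrative: at a true 70% and 60 subjects, false success rises from 5.7% to 10.0% or 16.2% if two or three failures are excluded, and not at all if one is. It rests on outcome-dependent exclusion, which the plan permits but does not plan. For MAE, only the estimate and upper limit could shift. The treatment of early re-intervention without a scan is an ambiguity to close rather than a stated rule. This should be fixed before the 12-month snapshot.

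**What to change.** Amend sections 11.1 to 11.3 and 11.6 as follows:

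1. Base the 30-day MAE rate on all enrolled subjects in whom the study device was introduced.
2. Base the 70% patency test on all subjects implanted with the study graft, regardless of deviations. Count any clinically driven re-intervention in the stented segment up to the 12-month assessment as a failure, with or without a duplex scan.
3. Leave out of that test only implanted subjects with no 12-month scan and no earlier failure, and list them with reasons.
4. Add a sensitivity analysis in all subjects in whom the device was introduced, counting non-implanted subjects and missing scans as failures.
5. Keep the per-protocol analysis as supportive, with its exclusion rules written and fixed before the snapshot.

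The cost is a text amendment and possibly slightly less favourable rates. No extra subjects are needed if 57 to 65 are analysed and true patency is 85%, since power then stays above the planned 80%. That assurance does not extend to 50 or 51 analysed, where power falls just below 80%.

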6.2 Enrollment

Subjects will be considered enrolled into the study once informed consent has been signed and all eligibility criteria confirmed. Investigators will access the target artery using standard percutaneous techniques and devices. Patient eligibility will be confirmed prior to insertion of the study device, based on procedural angiogram, sheath placement and wire placement across lesion followed by dilatation.

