To achieve 80% power using a one sided alpha of 0.05, with a clinically acceptable delta of 10%, a sample size is 50 subjects would be needed to reject the null hypothesis. The required sample size was calculating assuming a true performance rate for PQ Bypass of 85%, using the exact method (ref: Chow S.C. 2003 Sample Size Calculations in Clinical Research.), implemented using the PASS 12 software.

Table 23 : Superiority with PQ Bypass Performance of 85%

PG	PQ Bypass			
	80%	85%	90%	95%
70%	119	50	26	15
75%	441	103	42	21
80%	-	368	83	32
85%	-	-	283	60

However, due to noise in the literature, the fact that the true performance of the PQ Bypass Stent Graft is unknown at this time, and potential loss to follow up, a larger sample size is required for the Study in order to ensure 50 evaluable subjects taking into account the above assumptions. The lower the true performance rate of the PQ Bypass Stent Graft, the greater the sample size needed to reject the null hypothesis and maintain 80% power. Therefore, up to 65 subjects may be enrolled.

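### The intent-to-treat patency analysis has no rule for an enrolled subject whose graft is not implanted; as written, such a subject drops out of the denominator instead of counting as a failure

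*Combined protocol and SAP*

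**What the plan says.** Section 11.1 bases the assessment of device performance on a per-protocol analysis of the primary endpoints. It then adds the ITT analysis: "An Intent to treat analysis, along with other secondary analyses, will also be completed and reported". Neither analysis set is defined.

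On enrolment, Section 6.2 treats a subject as enrolled once consent is signed and all eligibility criteria are confirmed. On timing it says: "Patient eligibility will be confirmed prior to insertion of the study device". The same sentence bases that confirmation on the procedural angiogram, sheath placement, and crossing and dilating the lesion.

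On the endpoint, Section 5.2 requires "stent patency as evidenced by a peak systolic velocity ratio (PSVR) < 2.5 from DUS obtained within the 12 month visit window". A second condition is freedom from repeat procedures on the stented segment for clinical reasons. Section 11.1 reports the number and percentage of patent grafts. Its decision rule for the primary performance hypothesis is: "If the lower limit exceeds the performance goal rate of 70% the null hypothesis will be rejected and the endpoint will be met".

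On missing values, Section 11.6 rules out imputation and says: "Analyses will be performed with all available data only".

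Two further places matter. Section 19 defines primary patency by flow through the index lesion, without mention of the graft. It also defines acute technical success as successful delivery of the system and removal of the delivery system; that is a secondary endpoint.

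**The concern.** An ITT analysis of a device study should show what happens when treatment with the device is attempted, including attempts that fail. The main analysis here is per protocol, so the ITT analysis is the natural place to see whether the patency result survives once failed implants are counted. The plan gives these subjects no outcome. If they drop out, the ITT patency rate describes implanted subjects with a scan, and on this point it repeats the per-protocol result rather than testing it. At stake is the value of a supportive analysis, not the formal test.

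**Working it through.** **1. Can an enrolled subject leave without a graft?** Yes. Failure to cross or dilate the lesion is a failure of inclusion criterion 9 and of the eligibility check in Section 6.2, so it precedes enrolment. Failure to deliver or deploy the graft comes after enrolment. The gap is limited to this second group.

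**2. What endpoint value does that subject have?**
- Section 5.2 and the graft count in Section 11.1: with no stent and no stented segment there is nothing to classify, so there is no value.
- Section 11.6: no value is imputed, so the subject is absent from numerator and denominator.
- Section 19, index-lesion wording: if the lesion is treated with another device and the 12-month scan is satisfactory, the subject could be classed as patent.

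No passage says that the subject counts as not patent. Both readings give an ITT rate at least as high as one that counts the subject as a failure.

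**3. The plan's own figure.** Inputs from Section 11.1: "To achieve 80% power using a one sided alpha of 0.05, with a clinically acceptable delta of 10%, a sample size is 50 subjects" and "assuming a true performance rate for PQ Bypass of 85%, using the exact method". The score formula gives

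n = [(1.645·√(0.70·0.30) + 0.842·√(0.85·0.15)) / 0.15]² = 49.4, rounded up to 50.

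The exact binomial rule at n = 50 needs 41 successes, with one-sided alpha 0.040 and power 79.1%. The smallest n with at least 80% exact power is 49. The stated 50 is reproduced and is not in dispute.

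**4. Size of the effect.** The Wilson one-sided 95% lower limit for x successes in n, with p = x/n and z = 1.645, is

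L = [p + z²/(2n) − z·√(p(1−p)/n + z²/(4n²))] / (1 + z²/n).

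For 48/60: (0.8000 + 0.0225 − 0.0879) / 1.0451 = 0.703.
For 48/61: (0.7869 + 0.0222 − 0.0890) / 1.0444 = 0.689.

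Take 60 implanted subjects with scans, the plan's evaluable target, and 48 patent, the fewest that pass at n = 60. Let k further enrolled subjects have no implant. The value of k is an assumption; k = 5 reaches the enrolment cap of 65.

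| k | Rate, non-implants as failures | Lower limit | Above 70%? |
|---|---|---|---|
| 0 | 48/60 = 80.0% | 70.3% | yes |
| 1 | 48/61 = 78.7% | 68.9% | no |
| 2 | 48/62 = 77.4% | 67.6% | no |
| 3 | 48/63 = 76.2% | 66.4% | no |
| 4 | 48/64 = 75.0% | 65.2% | no |
| 5 | 48/65 = 73.8% | 64.1% | no |

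Dropping the non-implants gives the first row whatever the value of k.

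**5. Does one subject always matter?** No.
- With 65 enrolled and one non-implant, 51/64 has limit 70.3% and 51/65 has 69.0%. The limit crosses the goal.
- With 60 enrolled and one non-implant, 48 successes are needed whether n is 59 or 60: 48/59 has limit 71.7% and 48/60 has 70.3%, while 47/59 has 69.8% and 47/60 has 68.5%. Here one dropped failure cannot change the side of 70% on which the limit falls.

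**The case against.** The strongest reply is that nothing expressly excludes these subjects. The ITT set is undefined, Section 11.1 speaks of successful performance and of a system success rate, and a known failed deployment is not obviously missing data under Section 11.6. That stands as far as it goes: a sympathetic analyst could count the subject as a failure. But no rule requires it, and the endpoint wording and the graft count point the other way.

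Four stronger readings are tempting, and the documents do not support them.

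- *That an ITT analysis cannot include such a subject.* The index-lesion definition in Section 19 allows a reading that includes the subject, though possibly as patent.
- *That failed implants disappear from the study, or that ITT and per-protocol results must agree.* Failed deliveries count in acute technical success, for which Section 11.4 plans point estimates and confidence bounds. The two analyses could also differ through other protocol deviations.
- *That the sponsor's earlier study, STP 115, sets the precedent and the rate.* The footnote to Table 8 in Section 2.3 reads: "Excludes 1 subject who did not receive an implant and withdrew from the study post-discharge". That subject also withdrew, the table concerns safety, and the procedure was a percutaneous bypass with additional devices. One in 60 there is a weak guide to this study.
- *That the trial's error rate is inflated, or that the 30-day safety analysis has the same gap.* Device performance is assessed per protocol and the plan attaches no separate pass/fail rule to the ITT analysis. The safety composite of target lesion revascularization, amputation and death needs no graft, and Section 6.4 keeps all enrolled subjects in safety follow-up.

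**Conclusion.** The point holds for the ITT patency analysis. On the plain reading of Sections 5.2, 6.2, 11.1 and 11.6, a subject whose graft is not delivered or deployed after enrolment leaves the denominator; on the Section 19 reading the subject could even count as patent. If any such subject exists, the ITT rate is higher than one that counts the failed implant as a failure, or at best equal to it should a scan be read as not patent under the Section 19 wording.

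The size depends on a number that the documents do not give. In the boundary example, one to five non-implants lower the Wilson limit from 70.3% to between 68.9% and 64.1%. Away from such boundaries the side of 70% may not change. The example assumes that all 60 implanted subjects have a 12-month result. The stated sample size and the per-protocol test are unaffected, so this is a cheap improvement to a supportive analysis.

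**What to change.** In Sections 11.1 and 11.6:

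1. Define the ITT set as all enrolled subjects in whom insertion of the study device was attempted.
2. State, as an explicit exception to Section 11.6, that a subject without a successfully implanted study graft counts as not patent in the ITT analysis of primary effectiveness, whatever other treatment follows.
3. Report the number of non-implants beside the per-protocol result.

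The cost is a few sentences of plan text and no new data. The ITT patency figure becomes slightly less favourable if any implant fails. Section 11.1 says that the methods for the primary endpoints are fixed before analysis, so the rule should be written before the 12-month data snapshot.
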